2. LAY SUMMARY

Across England and Wales, over 10,000 patients have been treated for severe coronavirus disease 2019 (COVID-19) on an intensive care unit. Around 60% survived to leave hospital. We do not know how survivors' severe COVID-19 infection, or the treatment they received on the intensive care unit, will affect their long-term health. Understanding what happens to these patients can help us make sure they receive suitable care from their GP and other NHS services after they leave hospital.

This study will follow up survivors for 1 year after discharge from hospital. We will use data collected by the Intensive Care National Audit and Research Centre (ICNARC) to identify patients who were treated on an ICU for COVID-19. We will then use NHS data to see whether these patients were readmitted to hospital and why. Information from the Office of National Statistics will allow us to know whether these patients died. By linking different sources of patient data, we will be able to estimate the health risks faced by survivors of severe COVID-19. We will compare these risks to patients treated on an ICU for other conditions.

3. SYNOPSIS

Study Title	Outcomes of Patients who survived Treatment on an Intensive Care unit for COVID-19 in England and Wales: a comparative retrospective cohort study		
Internal ref. no. / short title	OPTIC-19		
Study registration	ClinicalTrials.gov:		
Sponsor	University of Oxford Clinical Trials & Research Governance, [name]		
Funder	The study is funded by the University of Oxford's COVID-19 Research Response Fund (Ref: 0009471).		
Study Design	Retrospective cohort study		
Study Participants	Patients aged 16 or over admitted as an emergency to an intensive care unit in England or Wales and discharged alive from hospital, and treated for either COVID-19 or another acute condition.		
Sample Size	319,600		
Planned Study Period	Project length: 36 months Follow up period: 1 year after discharge from an intensive care unit		
Planned Recruitment period	January 2016 to July 2020		
	Objectives	Outcome Measures	Timepoint(s)
Primary	To estimate the risk of death for patients who	Mortality	1 year

	survived to hospital discharge after treatment on an ICU for COVID-19 and compare these risks to patients treated on ICU as an emergency for other conditions		
Secondary	To estimate the risk of adverse events for patients who survived to hospital discharge after treatment on an ICU for COVID-19 and compare these risks to patients treated on ICU as an emergency for other conditions	
 • Emergency hospital admission • Emergency hospital admission for respiratory infection • Emergency hospital admission for a major adverse cardiac event (myocardial infarction, stroke, heart failure) • Emergency hospital admission for a venous thrombotic event (deep vein thrombosis or pulmonary embolism) • Development of end stage renal failure treated by renal replacement therapy 	1 year
Intervention(s)	Non-interventional study		

4. ABBREVIATIONS

CAG	Confidentiality Advisory Group
CCRG	Critical Care Research Group
CI	Chief Investigator
CMP	Case Mix Programme
COVID-19	COronaVirus Disease 2019
CRF	Case Report Form
CTRG	Clinical Trials & Research Governance, University of Oxford
HES	Hospital Episode Statistics
GCP	Good Clinical Practice
GP	General Practitioner

HRA	Health Research Authority
ICF	Informed Consent Form
ICNARC	Intensive Care National Audit and Research Centre
ICU	Intensive Care Unit
NHS	National Health Service
NICOR	National Institute for Cardiovascular Outcomes Research
RES	Research Ethics Service
OXTREC	Oxford Tropical Research Ethics Committee
PEDW	Patient Episode Database for Wales
PI	Principal Investigator
PIL	Participant/ Patient Information Leaflet
R&D	NHS Trust R&D Department
REC	Research Ethics Committee
SOP	Standard Operating Procedure
SSNAP	Stroke Sentinel National Audit Programme
UKOSS	UK Obstetric Surveillance System
UKRR	UK Renal Registry

5. BACKGROUND AND RATIONALE

Background

The severe acute respiratory syndrome coronavirus 2 (SARS-CoV-2) emerged in late 2019. By mid-July 2020 14 million people globally had been infected, of which over 600,000 died of coronavirus disease 2019 (COVID-19) (1). In the UK, nearly 20% of patients hospitalised with COVID-19 were transferred to an intensive care unit (ICU) or high dependency ward (2). In total, over 10,000 patients have been treated for COVID-19 on an ICU in England and Wales. On average, 50% of these patients survived to hospital discharge, although survival rates appear to be increasing (3,4). The long-term impact on the health of survivors is unknown.

Previous studies have shown that critically ill patients who survive ICU treatment are at greater risk of death and report lower health-related quality of life when compared with population norms (5–7). While pre-existing comorbidities partially account for these differences, organ damage caused by critical illness and the impact of intensive organ support given in the ICU likely also play a role (8). Analysis by the Intensive Care National Audit and Research Centre (ICNARC) suggests that patients admitted with COVID-19 receive higher intensity organ support and suffer more complications than observed in other viral respiratory infections (4). For example, nearly all COVID-19 patients required respiratory support, with nearly 60% receiving mechanical ventilation (compared to 43% with viral pneumonias) (4). Around one third of patients also required advanced cardiovascular or renal support (4,9). Cardiac (myocarditis, heart failure, arrhythmias, acute coronary syndrome) and venous thrombotic complications (e.g. pulmonary

embolism) were not uncommon (10–12). Although rare, some patients developed neurological complications such as stroke, encephalitis and Guillain-Barré syndrome (13).

Aim

This protocol describes a retrospective cohort study aiming to characterise outcomes for patients treated on an ICU with COVID-19 in England and Wales, one year after discharge from hospital. The study will use existing national audit data linked to routine healthcare datasets.

6. OBJECTIVES AND OUTCOME MEASURES

Objectives	Outcome Measures	Timepoint(s) of evaluation of this outcome measure (if applicable)

Primary Objective
 
To estimate the risk of death for patients who survived to hospital discharge after treatment on an ICU for COVID-19 and compare these risks to patients treated on ICU as an emergency for other conditions
	
Primary outcome
 
 • Death as recorded in the Civil Registration -- Deaths 	
1 year after discharge from ICU

Secondary Objectives
 
To estimate the risk of adverse events for patients who survived to hospital discharge after treatment on an ICU for COVID-19 and compare these risks to patients treated on ICU as an emergency for other conditions
	
Secondary outcomes
 
 • Emergency hospital admission • Emergency hospital admission for respiratory infection • Emergency hospital admission for a major adverse cardiac event (myocardial infarction, stroke, heart failure) • Emergency hospital admission for a venous thrombotic event (deep 	
180 days after discharge from ICU AND 1 year after discharge from ICU

	vein thrombosis or pulmonary embolism) 
 • Development of end stage renal failure treated by renal replacement therapy 	

Exploratory Objectives
 
To compare the risks in patients treated in ICU for COVID-19 to patients who survived to hospital discharge after treatment on an ICU for other bacterial or viral respiratory infections during the same period (January to June 2020)
 
To compare the risks in pregnant patients treated in ICU for COVID-19 with an age-matched control group
	
Primary outcome
 
 • Death as recorded in the Civil Registration -- Deaths 
Secondary outcomes
 
 • Emergency hospital admission • Emergency hospital admission for respiratory infection • Emergency hospital admission for a major adverse cardiac event (myocardial infarction, stroke, heart failure) • Emergency hospital admission for a venous thrombotic event (deep vein thrombosis or pulmonary embolism) • Development of end stage renal failure treated by renal replacement therapy 	180 days after discharge from ICU AND 1 year after discharge from ICU

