8. PARTICIPANT IDENTIFICATION

8.1. Study Participants

8.2. Inclusion Criteria

- Age ≥ 16 years
- Admitted to an adult, general ICU in England or Wales as an emergency (unplanned)
- Admitted to ICU for either:
 - confirmed COVID-19 between 1st January to 1st July 2020
 - without confirmed COVID-19 between 1st July 2016 and 1st July 2020

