11.4. Analysis populations

Primary group

Our primary group will be patients admitted with confirmed COVID-19 between 1st January to 1st July 2020.

Comparator groups

The primary comparator group will be patients admitted to ICU with viral or bacterial pneumonia between 1st July 2016 and 1st July 2019.

Secondary comparator groups will include:

- All emergency ICU admissions between 1st July 2016 and 1st July 2019
- All emergency ICU admissions between 1st July 2016 and 1st January 2020 where the primary diagnosis was not COVID-19
- All emergency ICU admissions between 1st January and 1st July 2020 where the primary diagnosis was not COVID-19

Pregnant patients

We will undertake a sub-group analysis in patients who were pregnant when treated for COVID-19 on ICU between 1st January and 1st July 2020.

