5.2. Assumed confounding covariates

The following variables are assumed to be related to the risk of experiencing one or more of the outcomes, and will therefore be included in the baseline characteristics table, be included as covariates in the multivariable regression models, and be included as covariates in the propensity scores.

- Patient demographics: age, sex, ethnicity, index of multiple deprivation (IMD), body mass index (BMI), clinical frailty score, smoking status, month of admission, dependency prior to ICU admission (fully/partial/total assistance with activities of daily living), geographical region
- Medical history: comorbidities (as per Elixhauser (14)), dialysis-dependent, total length of previous hospital admissions in year prior to ICU admission.
- Hospital/ICU stay characteristics: Length of hospital stay prior to ICU transfer, Length of ICU stay, length of hospital stay after discharge from ICU, hospital region, month of admission.
- Acuity: APACHE-II/ICNARC severity score at admission, length of mechanical ventilation, length of advanced organ support (cardiovascular, respiratory, renal, liver, neurological)

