5.3.2. Secondary outcomes

Cause-specific readmissions will be identified by combining HES (ICD-10) and GDPPR coding, using coding sets defined in Ayoubkhani et al. (15). For a venous thrombotic event, we will include the following ICD-10 codes: I80.0-I80.3, I80.8-I80.9, I82.9, O22.2-O22.3, O87.0-O87.1, I26.0, and I26.9.

• Emergency hospital admission – any non-elective hospital admission. Recorded in the hospital episode statistics data set.

- Emergency hospital admission for respiratory infection any emergency hospital admission for a respiratory infection.
- Emergency hospital admission for a major adverse cardiac event (myocardial infarction, stroke, acute heart failure)
- Emergency hospital admission for a venous thrombotic event (deep vein thrombosis or pulmonary embolism)
- Development of end stage renal failure treated by renal replacement therapy

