5.4.3. Comparison of COVID-19 cohort to other cohorts using propensity score matching

For each comparison of the COVID-19 cohort to a non-COVID cohort we will use propensity score matching to create cohorts that are similar in terms of baseline characteristics and confounding variables. We will construct a propensity score using logistic regression where the outcome is the cohort status, and the covariates will be those previously defined in Section 5.2. The model will allow for non-linear relationships between continuous variables and the outcome. The propensity score will then be estimated for each patient. One to one matching will be performed based on the

propensity score, initially using a nearest neighbour (greedy) approach. We will assess the balance achieved through the matching process using standard approaches, such as Q-Q plots, and assessments of the absolute standardised mean difference. If the covariates are not well balanced after nearest neighbour matching, alternative approaches will be tested, such as full matching, until sufficient balance is achieved. If sufficient balance cannot be achieved or too many patients from the COVID cohort are removed by the matching algorithm, we will consider using the propensity score for inverse probability weighting in our Cox regression models.

Once matched cohorts have been identified, we will analyse the outcomes with the standard regression modelling as described in Section 5.4.2– using Cox regression for the death outcome, and competing risk approaches for the secondary outcomes. However, since the data will now be clustered due to the matching, we will need to account for this in the regression models. We will therefore use cluster-robust standard errors.

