5.5. Subgroup analyses

For both the unadjusted and propensity-matched analyses, we will investigate the following subgroups: age, sex, ethnicity and length of advanced organ support.

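### The exploratory pregnancy comparison defines its controls only as age-matched, and later deliveries can count as emergency admissions almost only in the pregnant group

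*Protocol*

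**What the plan says.** The objective appears in the exploratory rows of Protocol 6 and SAP 1.2: "To compare the risks in pregnant patients treated in ICU for COVID-19 with an age-matched control group". Its outcomes are death and all five secondary outcomes, at 180 days and 1 year after ICU discharge.

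Protocol 11.4 describes only the exposed patients: "We will undertake a sub-group analysis in patients who were pregnant when treated for COVID-19 on ICU between 1st January and 1st July 2020". It names no control group for them.

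Protocol 11.1 leaves the detail to the SAP, but the SAP does not return to this comparison after stating the objective. SAP 4.4 defines four cohorts, none of them pregnant or age-matched. SAP 5.5 says "we will investigate the following subgroups: age, sex, ethnicity and length of advanced organ support"; pregnancy is not in the list. SAP 5.2 includes age and sex among the covariates, but not pregnancy, gestation or postpartum status. The eligibility criteria (Protocol 8.2, SAP 4.1.1) restrict neither sex nor pregnancy.

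SAP 5.3.2 defines emergency hospital admission as "any non-elective hospital admission. Recorded in the hospital episode statistics data set". Delivery and other maternity admissions are not set aside.

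Protocol 7.3 and 12.1 link UKOSS, by probabilistic matching, to identify patients pregnant at ICU admission. HES, the Maternity Services Data Set (MSDS) and PEDW are also on the linkage list.

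**The concern.** Two gaps combine.

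First, the contrast is not defined. One phrase fits at least two questions. With controls who did not have COVID-19, the target would be the effect of COVID-19 in pregnant ICU survivors. With non-pregnant COVID-19 controls, it would be the effect of pregnancy among COVID-19 survivors. These need different control groups, and the plan does not choose. Under the first question, non-pregnant or male controls would leave pregnancy and sex mixed with COVID-19. Under the second, male controls would leave sex mixed with pregnancy.

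Second, the stated outcome rule works against the comparison. A patient still pregnant at ICU discharge who goes home and is later admitted unplanned to deliver meets the emergency admission definition. Non-pregnant controls would rarely have that event. Under either question, a comparison with such controls would show an excess of adverse admissions that is partly just childbirth.

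At stake is the interpretability of one exploratory result, on the outcome likely to be commonest after death is set aside. The control group could also be settled after the data have been seen, which is what SAP 6 says pre-specification is meant to prevent.

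**Working it through.** **Figures in the plan.** The only stated size is the total: 90,000 × 3.5 = 315,000, and 315,000 + 4,600 = 319,600, which reproduces. No number of pregnant patients, event rate, effect size or control ratio is given for this comparison, so there is no figure of the plan's own to test.

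**What is and is not specified for the controls**

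| Feature | Stated? | Where looked for |
|---|---|---|
| Age | Yes, matched | Protocol 6, SAP 1.2 |
| Sex | No; a covariate for the main comparisons | SAP 5.2, 5.4.3 |
| Pregnancy status | No; in no covariate or subgroup list | SAP 5.2, 5.5 |
| COVID-19 status | No | Protocol 6, 11.4; SAP 4.4 |
| Admission period, ratio | No | Protocol 11.4, SAP 4.4 |

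**Does the main propensity analysis fill the gap?** SAP 5.4.3 begins: "For each comparison of the COVID-19 cohort to a non-COVID cohort we will use propensity score matching". It is not said to cover the pregnancy comparison. Suppose that it does. If the score is refitted with only pregnant patients as the exposed group, sex separates the groups and men drop out. If the pairs from the whole-cohort match are carried over, members of a pair need not share the same sex. Either way, pregnancy is not in the score, so controls are chosen without regard to it.

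**Delivery admissions: illustration with no true effect on any other admission.** All inputs here are assumptions.

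- r = 1-year risk of an emergency admission other than for delivery, the same in both groups: 0.2 to 0.4.
- q = share of the pregnant group with a later non-elective delivery admission: 0.1 to 0.5. This is the share who are still pregnant and deliver after leaving hospital, times the share of those admissions classed as non-elective. For example, 0.30 × 0.5 = 0.15 and 0.70 × 0.5 = 0.35.
- Controls are non-pregnant with no deliveries. The two kinds of admission are independent, and deaths are ignored.

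Risk in the pregnant group = 1 − (1 − r)(1 − q). Risk ratio (RR) = that risk / r. Risk difference = q(1 − r).

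| r | q | Risk, pregnant | RR | Difference |
|---|---|---|---|---|
| 0.4 | 0.1 | 1 − 0.6 × 0.9 = 0.46 | 0.46/0.4 = 1.15 | 0.06 |
| 0.3 | 0.3 | 1 − 0.7 × 0.7 = 0.51 | 0.51/0.3 = 1.70 | 0.21 |
| 0.2 | 0.5 | 1 − 0.8 × 0.5 = 0.60 | 0.60/0.2 = 3.00 | 0.40 |

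With pregnant controls who have the same r and q, the ratio is 1.0. It departs from 1.0 if the groups differ in the share still pregnant at discharge.

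**Sex mix, if not handled.** Let m be the male share of controls and s the male-to-female risk ratio. With no true effect, the expected ratio is 1/(ms + 1 − m). For m = 0.4 to 0.6 and s = 0.8 to 1.5 (assumed), the extremes are 1/(0.6 × 1.5 + 0.4) = 0.77 and 1/(0.6 × 0.8 + 0.4) = 1.14. This is smaller than the delivery effect over most of its range, and of either sign.

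**The case against.** The strongest reply is that the plan leaves a definition open and does not adopt a bad one. Much of that stands.

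- A reader might infer that controls are chosen by age alone, or that about half would be men. Neither document says so. Age matching is named and the rest is unstated; sex is a listed covariate and could enter through SAP 5.4.3.
- A reader might infer that pregnancy is identified only to pick out the COVID-19 subgroup. The UKOSS linkage is described without that limit. Its use for controls is unstated, not ruled out.
- A reader might infer that the comparison necessarily mixes pregnancy with COVID-19. That presumes controls without COVID-19. If the controls are non-pregnant COVID-19 patients, pregnancy is the exposure.
- A reader might see bias in the obstetric thrombosis codes (O22, O87), which men cannot receive. Controls' events are captured by the other codes on the list. Removing the obstetric codes could under-count events in pregnant patients.
- The objective is exploratory, and SAP 3.1 reports no p-values for secondary outcomes.

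The reply does not remove the delivery problem. The emergency admission rule is written and makes no exception, and no covariate in SAP 5.2 would correct it. It remains under either question whenever the controls are not pregnant. Choosing pregnant controls would largely remove it, but the plan does not do so.

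**Conclusion.** The point holds as an undefined comparison combined with an outcome rule that distorts one of its outcomes. The controls are specified only by age, the SAP contains no such analysis, and unplanned deliveries would count as adverse events mainly in the pregnant group.

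The size cannot be established from the documents. The spurious risk ratio of about 1.15 to 3.0 rests on assumed readmission risks of 20% to 40%, an assumed 10% to 50% with a non-elective delivery admission, and non-pregnant controls. It is on the risk scale, whereas the SAP will report hazard ratios. It also depends on how the hospital data class deliveries, which is not stated; if few are recorded as non-elective, the distortion is small.

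The delivery issue is confined to any emergency admission. Death and end stage renal failure are not affected by it, and the primary analysis is unaffected. The plan should be changed on this point, but it is not a threat to the study's main conclusions.

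**What to change.** 1. **Outcome.** For this comparison, exclude delivery admissions from the emergency admission outcome or report them separately, with the coding rule written into SAP 5.3.2. Keep the O22 and O87 codes in the thrombosis outcome.
2. **Question and controls.** Restrict controls to women, and state the question and the admission period in Protocol 6 and SAP 1.2.
   - If the question is the effect of COVID-19 in pregnancy, use age-matched women who were pregnant at emergency ICU admission without confirmed COVID-19. Identify pregnancy by the same rule in both groups from the linked HES, MSDS and PEDW data, with UKOSS as a supplement. Take account of pregnant versus postpartum status at discharge where numbers allow.
   - If the question is the effect of pregnancy among COVID-19 patients, use age-matched non-pregnant women with COVID-19.
3. **SAP.** Add the control cohort to SAP 4.4 and the analysis to SAP 5.5, and report the number of pregnant patients in each group.

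The cost is wording in both documents and some coding work on data sources already listed for linkage. The control group will be smaller than an age-only one, so intervals will be wider. Whether enough pregnant controls without COVID-19 exist cannot be judged from the documents and should be checked before the first option is adopted.

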7. STUDY DESIGN

7.1. Design

This is a retrospective cohort study of outcomes for patients treated on an ICU in England and Wales, one year after discharge from hospital. Our primary group will include patients admitted to ICU with confirmed COVID-19 between 1st January and 1st July 2020, who were discharged alive from hospital. We will use the ICNARC Case Mix Programme (CMP) to identify comparator groups of emergency ICU admissions, to which outcomes in the primary group can be compared. Once identified, each cohort will be linked to the national data sets to obtain information on subsequent hospitalisations, and longer-term mortality, cardiac and renal outcomes.

The study will be reported using the REporting of studies Conducted using Observational Routinely-collected health Data (RECORD) (14).

7.2. Setting

This study will use data from patients admitted to general adult ICUs in England and Wales, collected as part of the CMP. The CMP is an audit of patients admitted to adult general (and some specialist) ICUs that covers England, Wales and Northern Ireland. This study will only use data from ICUs in England and Wales, all of which have participated in the CMP programme since 2015.

